# 7.2 Formulation, Packaging, Labelling, Storage and Stability

EpiNet-First comprise pragmatic trials that use authorized drugs within the terms of marketing authorization. The EpiNet-First trials are therefore categorized as **Type A** with "no higher than the risk of standard medical care" (see section 12.1). All treatments will be taken as tablets and capsules already licensed to be used in the participant's country. There will be no modifications made to the products or their outer packaging, and therefore a pharmacy label is sufficient when the treatment is dispensed against a prescription.

The products can be dispensed by hospital and community pharmacies as they would be normally in clinical practice. It is the responsibility of the investigator to ensure that the GP is prepared to prescribe the remainder of any trial treatment not dispensed by the hospital pharmacy.

All treatments should be stored as per normal clinical practice. Please refer to the reference Medicine Data Sheets for your country; this should be kept within the site study file.

# 7.3 Preparation, Dosage and Administration of Study Treatments

All patients should be titrated to an initial maintenance dose, with dose adjustments made at subsequent appointments according to clinical response and adverse effects. Guidelines for titration and initial maintenance dose are outlined below. However, clinicians will be able to alter this to choose the titration rate and initial maintenance they think most appropriate for individual patients according to their usual practice. Doses outside the recommended range will be highlighted in EpiNet to check that the investigator has not made an error.

# **Recommended Titration and Initial Maintenance Doses for AEDs prescribed**

#### Levetiracetam

# Age > 12 years: Titration and Initial Maintenance Dose

250mg once per day for 2 weeks 250mg twice per day for 2 weeks 250mg morning and 500mg evening for 2 weeks 500mg twice per day - *initial target maintenance dose* 

#### Children aged 5-12: Titration and Initial Maintenance Dose

10 mg/kg/day as a twice daily regimen for 2 weeks
20 mg/kg/day as a twice daily regimen for 2 weeks
30 mg/kg/day as a twice daily regimen for 2 weeks
40 mg/kg/day as a twice daily regimen – *initial target maintenance dose* 

# Lamotrigine

# Age > 12 years: Titration and Initial Maintenance Dose

25mg once per day for 2 weeks

25mg twice per day for 2 weeks

50mg twice per day for 2 weeks

50mg morning and 100mg at night - initial target maintenance dose

# Children aged 5-12: Titration and Initial Maintenance Dose

- 0.5 mg/kg/day as a once a day dose for 2 weeks
- 1.0 mg/kg/day as a twice daily regimen for 2 weeks
- 0.5 mg/kg am and 1.0 mg/kg pm for 2 weeks
- 1.0 mg/kg am and 1.0 mg/kg pm for 2 weeks
- 1.5 mg/kg am and 1.5 mg/kg pm initial target maintenance dose

# Carbamazepine

# Age > 12 years: Titration and Initial Maintenance Dose

100 mg once per day for 2 week

100 mg twice per day for 2 week

100 mg mane, 200mg nocte for 2 weeks

200 mg bd thereafter – initial target maintenance dose

# Children aged 5-12: Titration and Initial Maintenance Dose

5 mg/kg/day for 2 week,

10 mg/kg//day for 2 week,

20 mg/kg/day thereafter – initial target maintenance dose

#### **Valproate**

# Age > 12 years: Titration and Initial Maintenance Dose

500mg once per day for 2 weeks

500mg twice per day - *Initial maintenance dose* 

# Children aged 5-12: Titration and Initial Maintenance Dose

10 mg/kg/day as a twice daily regimen for 2 weeks

15 mg/kg/day as a twice daily regimen for 2 weeks

25 mg/kg/day as a twice daily regimen – initial target maintenance dose

# 7.4 Unblinding

EpiNet-First trials are open-label trials and therefore unblinding is not required.

# 7.5 Accountability and Assessment of Compliance with Study Treatments

EpiNet-First trials are pragmatic rather than exploratory trials and the intention is to measure outcomes associated with treatment policies which reflect real life clinical practice. There are no formal accountability measures required for the trials, as treatments will be prescribed according to the local medical practices and dispensed by hospital and community pharmacies as would be normal in clinical practice.

It is accepted that, for a variety of reasons including perceived or actual efficacy and tolerability, not all patients will take their medicines as prescribed. Patients will be encouraged to take their medication as prescribed, and they will be asked about adherence, but no formal measurements of plasma drug levels are planned. The primary analyses will not be adjusted for actual or estimated adherence.

# 7.6 Concomitant Medications / Treatments

EpiNet-First trials are unblinded and therefore decisions about concomitant medications / treatments will depend on the local medical plan and clinical management.

#### 7.7 Dose Modifications

The aim of treatment will be to control seizures with a minimum effective dose of drug. This will necessitate dosage modification if further seizures or adverse events occur, as is usual clinical practice. The decision to discontinue allocated trial treatment is at the discretion of the treating physician and patient. Treatment may be discontinued at any point during the trial period for reasons such as inadequate seizure control, unacceptable adverse events, or any change in the participant's condition that the physician believes warrants a change in medication. Any changes in medication must be documented in the EpiNet record along with the reason for those changes. If a participant's treatment stops prematurely, the reason for discontinuation should be recorded in the EpiNet record, and the patient should still be encouraged to attend follow up visits for the remainder of the study.

At the end of trial participation the participants may continue their treatment as per local policy.

#### 7.8 Co-enrolment Guidelines

To avoid potentially confounding issues, ideally patients should not be recruited into other trials. Where recruitment into another trial is considered to be appropriate and without having any detrimental effect on the EpiNet-First trial this must first be discussed

with the coordinating centre who will contact the Chief Investigator ([name]).

#### 8 ASSESSMENTS AND PROCEDURES

Data will be entered directly into the EpiNet records, on-line. There are no separate Case Record Forms (CRFs) for data entry.

Participating centres will be expected to each maintain a file of essential trial documentation (Site File), and keep copies of all paper documents, including signed consent forms and seizure diaries for the trials.

Once the baseline information has been entered into the EpiNet record, the EpiNet-First algorithms will determine whether the patient is eligible for any of the EpiNet-First trials; if so, the patient will be randomised and followed-up in the trial. Each patient screened will be allocated a unique screening number, and each patient randomised will be assigned a unique subject number. Subject numbers will be trial-specific. For screening and randomisation procedures refer to section 6. For details of procedures associated with trial treatments refer to section 7.

Participant details including name, initials, date of birth and subject number will be reported on the consent form.

#### 8.1 Schedule for Follow-up

The expected duration of each participant is between a minimum of 2 years and a maximum of 5.5 years. All participants will be followed up whether they are still taking their allocated treatment or not. Where patients default from clinic follow-up, additional information will be sought from GPs, and where necessary patients will be contacted directly for follow up information.

Patients will be followed up at 3 and 6 months post randomisation, and at 6 month intervals thereafter, until the trial ends or they have been seizure-free for 2 years. Patients will be seen at other times as clinically indicated. The delegated member of the research team should update the EpiNet record whenever a patient is seen.

Where treatment is stopped the participant will be asked to continue with trial follow-up and attend the follow-up visits. If a participant does not wish to continue in the trial, a Consent Withdrawal form will be completed and EpiNet will be up-dated to capture the date and reason for trial withdrawal as detailed in section 5.3.2.

# **Table 1: Trial Assessments**

Follow Up Schedule

Procedures	Baselin e	T0+3	T0+6	T0+12 months + 6
Signed Consent Form	Χ			
Baseline data entered into	X			
Assessment of Eligibility Criteria	Χ			
Review of Medical History including:  Seizure history  Neurological insult Febrile seizures Family history of epilepsy FEG results (if possible) Further investigation (EEG / CT/MRI)	(X)			
Allocation of Study Treatment	Χ			
Review of seizure occurrence & hospital admissions		Х	Х	х
Review of Anti Epileptic Drug Use (Study Treatment & Concomitant):		х	х	Х
Assessment of QOL	Х	Х	Х	Х

X) – As indicated/appropriate.

 At baseline, all procedures should be done before study intervention.

# 8.2 Procedures for assessing Efficacy

Efficacy of the trial treatments will be measured through the period of the trial using a number of measures.

#### 8.2.1 Seizure Diaries

Data on seizures recorded in patient seizure diaries, including number, type and date, will be captured at follow up visits and transcribed to the EpiNet record.

# 8.2.2 Quality of Life Scores

The VAS score of the QOLIE31 (Section 8.4) obtained throughout the trial can be used as a subjective measure of efficacy.

# 8.3 Procedures for Assessing Safety

Only Serious Adverse Events will be reported, using a special Serious Adverse Event form in the EpiNet record. As well as reporting these to the Trial Coordinating centre, serious adverse reactions should also be reported to the relevant authorities in the Investigator's own country.

#### 8.4 Quality of Life Assessments

Adult patients (18 years and over) will be asked to complete the Visual Analogue Scale from the QOLIE 31 questionnaire(37). Participants aged 16-17 will complete the QOLIE-AD-48 for adolescents. Parental proxy reports of (health-related) quality of life will be used for those under age 16 (38).

The Visual Analogue Scale (VAS) to be completed at baseline will be provided to the participant and / or parent as applicable on the day of randomisation by a member of the research team. The VAS should also be completed at each study visit where possible.

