# 6.2 Baseline

Once consent has been obtained from the patient (or parent / legal representative where applicable, and assent by the child where appropriate and applicable) the delegated member of the research team e.g. research nurse/consultant should record the required baseline data (which will include seizure history, history of neurological insult, febrile seizures, family history of epilepsy, EEG and imaging (CT or MRI) results) into the EpiNet record. If further investigations (EEG or imaging) are requested at this visit, data on results will be collected when available, but randomisation need not be delayed. If the patient is confirmed eligible then the research team should proceed to randomise the patient.

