#### 6.3 Randomisation

Patients **should not** be randomised until:

- a) Consent has been obtained from the patient (parent / legal representative where the patient is under 16 years of age)
- b) The minimum baseline data has been recorded into the EpiNet record;
- c) Eligibility criteria have been fulfilled.

The trial in which the patient will be enrolled will be determined by the seizure type and the willingness of the patient to take valproate. Investigators will be guided through this process by algorithms within the EpiNet database. Investigators will be asked what type of seizures the patient has, and whether the patient would be willing to take valproate. Patients will then be randomised to one of the following treatments:

For each of the trials, randomisation will be by block randomisation with variable block size to minimize any potential for predicting allocation. Randomisation will be stratified by country, age (below 18 vs 18 or older) and sex.

Patients who have focal seizures will be entered into the **EpiNet-First Trial 1**, and randomised to receive either levetiracetam or lamotrigine or carbamazepine (in a 1:1:1 ratio).

Patients who have generalised seizures (excluding patients who have a focal onset to their seizures, or who have absence seizures alone) who are willing to take valproate will be entered into the **EpiNet-First Trial 2** and randomised to receive either levetiracetam or valproate (in a 1:1 ratio),

Patients who have generalised seizures (excluding patients who have a focal onset to their seizures, or who have absence seizures alone) who are NOT willing to take valproate will be entered into the **EpiNet-First Trial 3** and randomised to receive either levetiracetam or lamotrigine (in a 1:1 ratio)

Patients who have seizures of uncertain nature who are willing to take valproate will be entered into the **EpiNet-First Trial 4** and randomised to receive either levetiracetam or lamotrigine or valproate (in a 1:1:1 ratio).

Patients who have seizures of uncertain nature who are NOT willing to take valproate will be entered into the **EpiNet-First Trial 5** and randomised to receive either levetiracetam or lamotrigine (in a 1:1 ratio).

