Participants will be randomised from within the EpiNet database, using a secure (24-hour) web based randomisation programme. Personal login username and password will be required to access the EpiNet database and the web-based randomisation system. When eligibility has been confirmed the participant will be randomised. Treatment allocation will be displayed to the authorised randomiser on a secure webpage within the EpiNet record, and an automated email confirmation will be sent to the authorised EpiNet investigator, PI and the trial coordinator.

If there are any problems with the randomisation systems, please contact the EpiNet-First coordination service via e-mail: [contact]

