#### 7. TRIAL TREATMENTS

#### 7.1 Introduction

EpiNet-*First* comprises five randomised controlled trials run in parallel. Depending on the specific trial, patients will be randomised to receive either levetiracetam, lamotrigine, carbamazepine or valproate.

Randomised treatment should begin within 7 days of randomisation. The research team should ensure that any delay before starting the trial treatment does not impact on the well-being of the participant. Assessments that should be carried out prior to the start of the randomised treatment are detailed in sections 6 and 8.

All treatments will be prescribed and issued as per routine practice. Generic versions of AEDs can be prescribed, if these are routinely used in a particular centre. Specific details regarding which version of an AED is used will be recorded.

If a patient has already been commenced on an AED, he can only be recruited for any of the EpiNet First trials if:

- he/she has taken the AED for 7 days or less;
- he/she agrees to be randomised to one of the treatment arms for the trial for which the patient is eligible. (In some circumstances, it may be possible for the patient to be randomised to the drug which he/she is already taking.)
- the investigator considers that it is appropriate to include the patient in the trial.

In these circumstances, if a patient is randomised to another AED, the original AED should be withdrawn according to the investigator's standard clinical practice. In most circumstances, since the patient will have used the drug for only a few days, it will be appropriate to discontinue the AED immediately. The new AED (to which the patient has been randomised) will be introduced according to routine clinical practice. If appropriate, the two drugs can be overlapped for a brief period. Full details including the dates on which the original AED was commenced and discontinued, and the dose used, should be recorded in the EpiNet record.

If a patient is randomised to the same AED that he / she was already taking, the drug should simply be continued and/or increased according to routine practice. The date on which the patient started the drug should be recorded in the EpiNet record, even if that date is earlier than the date of randomisation. Outcome data will be calculated from the date of randomisation.

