# 9.5 Analysis Plan

All participants who are invited to participate in EpiNet-First trials will be accounted for and a CONSORT statement prepared. A table summarizing the number of participants who have assessed for eligibility, registered in each trial and been randomized for participation, will be provided. Participant disposition will be presented in one or more figures.

Demographic data collected on all randomised participants will be summarized. Summaries of continuous variables which are normally distributed will be presented as means and standard deviations or medians and inter-quartiles for skewed data, while categorical variables will be presented as frequencies and percentages.

Treatment evaluations will be undertaken for each trial separately. The primary outcome will be summarised by Kaplan-Meier curves and compared between the treatment groups using the log rank test. Cox proportional hazards regression models will be used in two different ways: (i) including the treatment effect only, using treatment indicator variables (ii) including the treatment effect together with stratification factors and important baseline covariates. The impact of country effect on the treatment comparison will be controlled by considering a random effect in the regression analysis. A similar analysis strategy will be employed for the other secondary time to event outcomes. For time to treatment failure, further analysis will be undertaken to assess the two main reasons for treatment failure-inadequate seizure control and unacceptable adverse effects. To allow for possible dependence between the different withdrawal risks, cumulative incidence analyses will be presented(39).

The proportion of patients who achieve a 12 month remission by 18 months who have not changed to a different AED will be compared between treatment groups using simple chi-squared test with estimation of relative risks and 95% confidence EpiNet-First Study Protocol Version 1.0 Dated 15/04/14

intervals. Logistic regression analysis will also be conducted adjusting for stratification factors and important baseline covariates.

QOL data will be analysed longitudinally to explore between treatments differences in scale scores overtime, taking account of stratification factors, baseline QOL and other important covariates. Line listings will be prepared for all serious adverse events.

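### The protocol lets baseline quality of life be scored after the open-label allocation is known, then uses it as an adjustment covariate

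*Protocol*

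**What the plan says.** All references are to the protocol.

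- **When the form is given.** On the Visual Analogue Scale (VAS), section 8.4 says that the form "to be completed at baseline will be provided to the participant and / or parent as applicable on the day of randomisation". It gives the day, not the order relative to allocation.
- **The timing rule.** The footnote to Table 1 reads "At baseline, all procedures should be done before study intervention". Section 7.1 uses the same anchor: "Assessments that should be carried out prior to the start of the randomised treatment are detailed in sections 6 and 8".
- **What must come before randomisation.** Section 6.3(b) requires that "The minimum baseline data has been recorded into the EpiNet record". Section 6.2 describes the baseline data as information "which will include seizure history, history of neurological insult, febrile seizures, family history of epilepsy, EEG and imaging (CT or MRI) results". Neither names QOL.
- **When the allocation becomes known.** Section 6.3 states: "Treatment allocation will be displayed to the authorised randomiser on a secure webpage within the EpiNet record". Section 7.4 confirms that the trials are open label.
- **How baseline QOL is used.** Section 9.5 has QOL analysed longitudinally, "taking account of stratification factors, baseline QOL and other important covariates".
- **What rests on QOL.** It is secondary endpoint (h) in section 4.2. Section 8.2.2 offers the VAS as a subjective measure of efficacy. Section 10 relies on QOL to weigh overall tolerance of a drug against seizure control, since non-serious adverse events are not collated as an endpoint.

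**The concern.** A baseline covariate is safe to adjust for because the treatment cannot have influenced it. That holds when it is measured before allocation, or when the allocation is concealed from whoever scores it. Here neither is assured. The VAS is a subjective self-report, replaced by a parent's report for patients under 16, and the allocation is disclosed as soon as the patient is randomised.

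Expectations that differ by drug are plausible on the protocol's own account. Section 2.2 reports that many investigators regard carbamazepine as first choice for focal seizures, and that valproate is widely seen as the drug of choice for generalised seizures. Patients or parents who learn the allocation in that setting could rate the same day differently by arm. The covariate then carries part of the effect of allocation, and adjusting for it moves that part, with reversed sign, into the treatment comparison.

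At stake is the QOL comparison, one of the protocol's measures of everyday tolerability. The order of completion is a matter of data collection. The protocol asks for no record of whether the form was completed before or after the allocation was seen, so an analysis plan written later could not reliably identify or repair affected baselines.

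**Working it through.** No stated figure needs reproducing. The check is of the order of events and of what follows from it.

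**Step 1: is scoring after allocation permitted?** Take a site that obtains consent, records the clinical history, EEG and imaging, randomises, tells the patient the drug, and hands over the VAS at the same visit.

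| Requirement | Source | Met? |
|---|---|---|
| VAS provided on the day of randomisation | 8.4 | Yes |
| Baseline procedures before study intervention | Table 1 footnote | Yes, no dose of the allocated drug has been taken |
| Minimum baseline data recorded before randomising | 6.3(b) | Yes, as far as the items named in 6.2 go |
| Consent and eligibility before randomising | 6.3(a), (c) | Yes |

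No written rule is broken. Table 1 marks QOL in the baseline column, on a row separate from baseline data entry, and this does not settle the order.

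**Step 2: does the order matter for the planned analysis?** For two arms, with T = 1 or 0 for treatment, let

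- X0 be the score that would be given before allocation is known;
- d be the between-arm difference in how far knowing the allocation shifts the baseline score;
- e be the between-arm difference in how far expectation shifts the follow-up score;
- b be the slope of follow-up on baseline within arms;
- τ be the treatment effect free of expectation.

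The recorded baseline is X = X0 + d·T (leaving out any shift common to both arms), and the follow-up score is Y = τ·T + b·X0 + e·T + error. Substituting X0 = X − d·T gives

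Y = (τ + e − b·d)·T + b·X + error.

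The adjusted treatment coefficient is therefore τ + e − b·d.

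**Step 3: what follows?**

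- The term due to a post-allocation baseline is −b·d.
- If knowing the allocation moves all arms equally, d = 0 and the term vanishes.
- If baseline is scored before allocation is displayed, d = 0 in expectation, by design.
- The term e comes from open-label follow-up scores. It is there whenever baseline is taken, and reordering the baseline does not remove it.
- The net departure from τ is e − b·d, so its sign and size cannot be stated without e.

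The documents give none of b, d or e, so no number is put in.

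**The case against.** The strongest reply is that the protocol, read as a whole, already puts baseline QOL before randomisation. The list in section 6.2 is introduced as what the data will include, so it is not exhaustive. Section 6.2 has baseline data recorded and eligibility confirmed before the team randomises. Section 8 has baseline information entered before the eligibility algorithm runs. Table 1 and section 8.4 both call the VAS a baseline item, and EpiNet's mandatory fields are not visible here. This stands in part: many sites may well score QOL first, and a reader should not infer that section 6.3(b) excludes it. But nothing says that it is included, and the one explicit rule sets the weaker anchor.

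Second, follow-up scores are open label too. If e has the same sign as d and exceeds b·d/2, the affected baseline gives a smaller absolute departure from τ than a clean one would. That is correct, and is why no direction is claimed. It would be a chance cancellation, not a reason to leave the order open.

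Third, the scope is narrow. QOL is the last of eight secondary endpoints, and tolerability is also measured by time to treatment failure due to unacceptable adverse events. Eligibility requires that each drug in the trial be considered appropriate, which should dampen disappointment. All of this stands and limits the weight of the point.

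Two stronger readings are tempting but unsupported. 

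- From "Randomised treatment should begin within 7 days of randomisation" a reader might infer that the form may come back days later. That interval concerns the drug; section 8.4 ties the VAS to the day of randomisation. 
- A reader might also infer that patients already taking an antiepileptic drug cannot meet the Table 1 footnote. Section 7.1 distinguishes a drug started earlier from the randomised treatment and already asks for its start date. Such exposure precedes randomisation and is balanced in expectation.

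**Conclusion.** The point holds as a matter of what the protocol permits. Baseline QOL may be scored after an open-label allocation is known, and section 9.5 then adjusts for it. The defect is that the stated anchor is the start of treatment, whereas a subjective covariate in an open-label trial needs to be anchored before disclosure of the allocation.

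The size is unknown. Bias from this source requires that some sites do score after allocation and that knowing the drug shifts scores differently by arm. A reader might want to attach a figure in VAS points, but any such figure would rest wholly on assumed values of b, d and e. The primary endpoint, time to 12 month remission, and the sample size are untouched. The change is worth making because it is nearly free and has to be made before data are collected.

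**What to change.** - **Section 8.4 and the Table 1 footnote:** state that the baseline QOL instrument is completed after consent and before the allocation is displayed.
- **Sections 6.2 and 6.3(b):** name baseline QOL among the data recorded before randomisation, with a not-obtained option so that a missing form does not block randomisation.
- **Section 8.4 or 9.5:** state that a QOL score completed after allocation is not used as baseline.

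The cost is wording and one EpiNet field. No extra visit, instrument or patient is needed, since the form is already due that day. The downside is a few minutes before randomisation and an occasional missing baseline. The change does not remove expectation effects on open-label follow-up scores, which remain a limitation when QOL is interpreted.
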